Phase I: Study participants will complete a one-time study visit and will be asked to rinse/gargle with 10ml of the assigned mouthwash for 30 seconds. Subjects will be randomized to either rinse/gargle with Povidone-iodine 0.5% or a placebo. Phase II: Study participants will be given a 1 week supply of Povidone-iodine 0.5% mouth rinse and will be asked to rinse/gargle with 10ml for 30 seconds 4 times per day. Subjects will be contacted on Day 7 using Telemedicine, phone calls, and/or text messages to determine clinical status.

Study duration

Phase I: 1 day Phase II: 1 week

Characteristics of the Study Population

Target population

Forty (40) subjects with confirmed clinical diagnosis of COVID-19 and at least one onset clinical sign will be recruited and randomized in the study. If there are screen failures, more than 40 subjects may consent. Subjects who sign the informed consent form and are randomized and receive the study product, and subsequently withdraw, or are withdrawn or discontinued from the study, could be replaced at the investigators discretion. For example, if a subject's samples are found to be less than optimal.

Subjects enrolled by Penn Researchers

40

Key inclusion criteria

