1. Able and willing to provide informed consent prior to initiation of study procedures. 2. Stated willingness to comply with all study procedures and availability for the duration of the study. 3. Male or female, aged 18 years and older. 4. Clinical diagnosis of COVID-19 infection confirmed with a positive point of care test. 5. Confirmed diagnosis within 5 days of baseline visit (within 5 days of COVID-19 test) and at least one clinical COVID-19 symptom [*Signs and symptoms of COVID-19 present at onset, but over the course of the disease, most people will experience the following: fever or chills, cough, shortness of breath or difficulty breathing, fatigue, muscle or body aches, headache, new loss of taste or smell, sore throat, congestion or runny nose, nausea or vomiting and diarrhea.] 6. Presents with a minimum of six natural teeth. 7. Ability to rinse/gargle with study products. 8. Not using mouth rinse/gargling solutions at the time of enrollment. 9. Not taking antimicrobial medications (antibacterial, antiviral, antibiotics, including hydroxychloroquine) at time of enrollment. 10. Ability to participate in the study and come to site during Phase I of the study for collection of swabs and saliva. 11. Willing to use an acceptable method of birth control throughout duration of the study. Acceptable methods include hormonal contraceptives, barrier methods, abstinence, or other effective methods approved by the PI. 12. If continuing to Phase II of the trial, ability to continue using study products for 1 week (+ 3 days). (Participants do not have to agree to participate in Phase II in order to participate in Phase I.) 13. If continuing to Phase II of the trial, agree to receive text messages/phone calls containing questionnaires regarding compliance and use of study product, and reminders, able to complete virtual follow-up study visit for collection of outcomes data.

Key exclusion criteria

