Baseline/Visit 1 can be done in one visit with confirmatory diagnosis of COVID and after inclusion/exclusion is met. If a subject is a screen failure during Phase I for any reason and is unable to be enrolled, they will receive \$20. Phase I: \$100 Phase II: \$20 for attending the remote visit on Day 7 Subjects will be compensated through Greenphire ClinCard. If a subject does not have a social security number, he/she will be compensated via an Amazon gift card.

Study Procedures

Procedures

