At the Screening/Baseline visit, the following procedures will be performed: Informed consent will be obtained; Demographic information will be obtained; Vital signs measurements will be performed (temperature, blood pressure, heart rate, height, weight); Oral health questionnaire; A clinical oral exam will be completed; Dental and Medical history will be reviewed to determine eligibility based on inclusion/exclusion criteria; A point of care COVID-19 test will be completed to determine eligibility based on inclusion/exclusion criteria; Premenopausal women of child bearing potential will complete a urine pregnancy test to confirm eligibility; Eligible subjects will be randomized to one of two treatments; Randomized subjects will rinse with 10 ml of their assigned product for 30 seconds; Swab samples (posterior dorsal tongue and nasal swabs) will be collected at Baseline (pre-rinse) and at 5, 30 and 60 minutes post-rinse; Salivary samples will be taken at Baseline (pre-rinse) and at 5, 30 and 60 minutes post-rinse; Subject who successfully complete Phase I will be invited to continue into Phase II of the clinical trial and given the product to take home to use as instructed. If continuing they may be scheduled for a remote follow-up visit on Day 7. If not continuing the subject will be exited from the clinical trial after Visit 1. Phase II Visit 2 (Day 7 +/- 3 Days): Medical history will be updated. This visit will be completed remotely via the collection of questionnaires. Subjects will be sent a link to the questionnaires via text message or email, and/or be contacted via phone or telemedicine. Questionnaires will collect outcomes data assessing their clinical status, number of COVID-19 symptoms, symptoms onset and the severity of symptoms. At this timepoint subjects will exit the study. A separate modification request will be submitted at the time a pregnancy is identified, before any follow-up on incidental pregnancy will occur. At that time, the pregnancy supplemental form, along with a description of the data and method of collection (i.e. via self-report, medical chart review, questionnaires, etc.) will be provided.

STATISTICAL CONSIDERATIONS

Statistical Hypotheses (Phase 1 ONLY)

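### The Visit 2 window lets the exit contact, the only scheduled adverse-event query after take-home rinsing begins, fall as early as Day 4 of a one-week course

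*Combined protocol and SAP*

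**What the plan says.** All references are to the combined protocol and SAP.

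- **Supply and dose.** Study Design (Design): "Study participants will be given a 1 week supply of Povidone-iodine 0.5% mouth rinse", to be used 4 times a day. Study duration puts Phase II at one week.
- **Target day.** The same Design section says "Subjects will be contacted on Day 7 using Telemedicine, phone calls, and/or text messages to determine clinical status". Subject compensation pays "for attending the remote visit on Day 7", and Secondary outcome variable(s) names clinical status at that day.
- **Permitted window.** Study Procedures (Procedures): "Phase II Visit 2 (Day 7 +/- 3 Days): Medical history will be updated". At that contact, "Questionnaires will collect outcomes data assessing their clinical status, number of COVID-19 symptoms, symptoms onset and the severity of symptoms". The section then states: "At this timepoint subjects will exit the study".
- **Product use.** Key inclusion criteria, item 12: "If continuing to Phase II of the trial, ability to continue using study products for 1 week (+ 3 days". This tolerance has a plus side and no minus side. Study Procedures says continuing subjects are "given the product to take home to use as instructed"; the instructions themselves are not set out.
- **Safety collection.** Safety Analyses has adverse events asked about at each study visit. It adds medical-record review for as long as the study lasts, and has subject-reported and evaluator-observed events entered on the case report form. Gingival or mucosal irritation and allergic reaction are the expected related events.

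**The concern.** The window for the visit and the tolerance for product use do not match. Product use may run over a week but is not expected to fall short of one, while the contact that closes the study may come three days before the week is up. Nothing ties the contact to the last rinse. Nothing says whether a subject who exits early keeps rinsing, stops, or returns the product.

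Two things are at stake, both in Phase II. First, irritation from repeated rinsing could start late in the course, after the only scheduled occasion on which a home user is asked about adverse events. If use instead stops at exit, the course is cut short. Second, an outcome defined at Day 7 could be recorded on Day 4 of an acute illness. The second point holds whether or not rinsing continues.

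**Working it through.** The documents state no rinse total, so there is no figure of the plan's to reproduce. The check is schedule arithmetic.

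**Inputs.** 4 rinses a day and a one-week supply (Design); target Day 7 with a tolerance of 3 days either way, and exit at the contact (Procedures).

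**Assumptions.** Four rinses are taken on each of seven consecutive days. The documents do not give the first day of home use, so both Days 0-6 and Days 1-7 are shown. They also do not give the time of the contact, so it is placed either before or after all of that day's rinses.

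**Formulas.**
- Course = 4 × 7 = 28 rinses.
- Earliest contact = 7 − 3 = Day 4; latest = 7 + 3 = Day 10.
- For a contact on Day c and first use on Day s, rinses done = 4 × (c − s + 1) if the contact follows that day's rinses and 4 × (c − s) if it precedes them, capped at 28. Rinses left = 28 − rinses done.

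For Day 4 with s = 0: 28 − 20 = 8 (after) or 28 − 16 = 12 (before). With s = 1: 28 − 16 = 12 (after) or 28 − 12 = 16 (before).

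| Contact day | Left, contact after that day's rinses (s = 0 / s = 1) | Left, contact before them (s = 0 / s = 1) |
|---|---|---|
| 4 | 8 / 12 | 12 / 16 |
| 5 | 4 / 8 | 8 / 12 |
| 6 | 0 / 4 | 4 / 8 |
| 7 (target) | 0 / 0 | 0 / 4 |
| 8 to 10 | 0 / 0 | 0 / 0 |

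At Day 4 the range is 8/28 = 29% to 16/28 = 57%. At the Day 7 target it is 0 to 4/28 = 14%. If use stops at exit, the same counts are rinses not taken, and a Day 4 exit ends the course at 28 − 16 = 12 (43%) to 28 − 8 = 20 (71%) of 28.

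**Is there another scheduled query?** There are two visits. Visit 1 comes before any home use. The texts and calls in inclusion item 13 concern compliance, product use and reminders; adverse events are not named. Secondary outcome variable(s) has symptoms gathered over the whole of Phase 2, but these are COVID-19 symptoms, and the only outcome collection described is Visit 2. That leaves Visit 2 as the one scheduled adverse-event query covering home use.

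**The case against.** The strongest reply is that Day 7 is the target throughout, and that a symmetric tolerance is ordinary scheduling which keeps assessments centred on the outcome day. On the target day almost nothing is left of the course. The safety gap also needs two things to happen, an early contact and continued rinsing after exit, and the documents establish neither. This stands as a limit on weight. It does not change what the window permits.

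There is also partial cover. Medical records and subject reports may pick up some events, and the take-home instructions, which are not in these documents, may say when to stop. These narrow the gap. Nothing says that record review or reporting continues after exit.

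Three stronger readings are tempting and are not supported.

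- A reader might infer that Visit 2 is the only adverse-event query after baseline. Visit 1 runs to 60 minutes after the Phase I rinse, and events are asked about at every visit, so that visit can include a post-rinse query. The gap concerns home use only.
- A reader might take 8 to 16 uncovered rinses as the usual case. That is the Day 4 extreme, and nothing shows how often contacts would come early.
- A reader might count ten days of use from item 12. At 4 a day that is 40 rinses, more than the 28 in a one-week supply. Use stretched past Day 7 would leave more rinses after an early contact, and perhaps some after Day 7, but the documents do not support a count.

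**Conclusion.** The point holds as a minor one, to consider. Followed as written, the protocol allows the exit contact from Day 4. On a 28-rinse course at 4 a day, 8 to 16 rinses then remain, against 0 to 4 at the Day 7 target and none from Day 8. Those rinses are either taken with no scheduled adverse-event query to follow or not taken at all; the documents do not say which. Day 7 clinical status may also be a Day 4 reading.

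Confidence is high about what the text permits and about the counts on their stated assumptions. It does not extend to how often the problem would arise. Phase II is open label with all subjects on active product, and the statistical hypotheses cover Phase I only. The Phase I primary endpoint is not affected.

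**What to change.** Amend the Visit 2 window to Day 7 + 3 days, and add the following:

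- Subjects finish the one-week supply and stop by the end of Day 7, or at the latest before the contact.
- The contact is held after the last rinse, and the subject exits only then.
- No product is used after exit.
- If the contact is later than Day 7, the questionnaire asks for clinical status as of Day 7.

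The stopping rule matters. If use could run to Day 10 under item 12, a contact held after the last rinse would be confined to that one day.

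The cost is a wording amendment and one questionnaire instruction, with the same single remote contact. The contact window becomes 4 days (Days 7 to 10) instead of 7 (Days 4 to 10), with slightly more risk of a missed contact. Day 7 status may be recalled up to 3 days later.

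Two smaller remedies do less. Keeping the window and telling subjects to stop at exit removes unqueried exposure but accepts a shortened course. Adding an adverse-event question after the last rinse covers the exposure but needs a further contact when Visit 2 has come early. Neither stops Day 7 status being recorded on Day 4.

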1. Individuals receiving antiviral medications 2. Pregnant or breastfeeding women (for premenopausal women of childbearing potential, pregnancy status to be confirmed through a urine pregnancy test during the study visit) 3. Inability to comply with study protocol 4. Having an allergy to any of the study mouthwash ingredients 5. Having any thyroid condition. 6. Presents with a current suspicious oral lesion at the examiners discretion, and/or currently undergoing radiation therapy for head or neck cancer, and/or has received radiation therapy to the head or neck (including radioactive iodine therapy).

Populations vulnerable to undue influence or coercion

Although not directly targeted, mentally disabled persons, economically or educationally disadvantaged person, and/or employees or students of the University of Pennsylvania will not be denied enrollment and any special protections an/or additional safeguards will be undertaken in order to protect the rights and welfare of these subjects from coercion or undue influence as appropriate.

Subject recruitment

COVID-19+ patients will be recruited to achieve 40 study subjects who enroll in and are eligible for study participation. Primary recruitment will be through the University of Pennsylvania testing sites. We will also place flyers within our hospitals and dental clinics, including our community health centers outside the school. Subjects who present a positive COVID test and at least one COVID symptom (see inclusion criteria) will be recruited. Email messages advertising using an IRB approved template the study will also be sent out to University of Pennsylvania mailing lists that include faculty, staff, and students.

Will the recruitment plan propose to use any Penn media services (communications, marketing, etc.) for outreach via social media avenues (examples include: Facebook, Twitter, blogging, texting, etc.) or does the study team plan to directly use social media to recruit for the research?

Yes

Subject compensation*

Will subjects be financially compensated for their participation?

Yes

If there is subject compensation, provide the schedule for compensation per study visit or session and total amount for entire participation, either as text or separate document

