For the study, the null hypothesis (H_0): $\delta = 0$ and the alternative hypothesis (H_1): $\delta \neq 0$. The type of comparison in all cases will be superiority. Our primary endpoint is the percentage reduction of SARS-Co-V-2 load at 60 minutes (post-intervention) compared to baseline between the PVP-I mouthwash versus the placebo mouthwash. The secondary endpoints are the respective percentage reductions of SARS-Co-V-2 load at both 5 and 30 minutes (post-intervention) compared to baseline between the PVP-I mouthwash versus the placebo mouthwash.

Sample Size Determination

Assumptions:

- Looking to determine the value of the difference in the percentage reduction of SARS-Co-V-2 load at 60 minutes (post-intervention) compared to baseline between the PVP-I mouthwash versus the placebo mouthwash.
- Will use a two sample t-test assuming equal variance and sample size in each of the two arms
- δ is the difference between population means at which power and sample size calculations are made.
- Null hypothesis (H_0): $\delta = 0$, Alternative hypothesis (H_1): $\delta \neq 0$
- Trying to determine necessary sample size to show a significant difference under the alternative hypothesis by assuming a 20% greater difference (PVP-I versus placebo) in the reduction of SARS-Co-V-2 load after 60 minutes and a corresponding standard deviation for both groups of 0.20.
- Alpha (probability of Type-I error [true null hypothesis is rejected]) of 0.05
- Power (probability of rejecting a false null hypothesis) of 0.80
- We will assume 20% dropout rate in calculating the final # of patients to be enrolled

For the desired 80% power, the necessary sample size(s) is calculated to be n=34 (17 per arm). After accounting for the aforementioned 20% dropout, 44 patients will be enrolled in the study (22 per arm). The power calculations were performed using PASS Software 20.0.3.

General Approach

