Descriptive statistics will be used to compare characteristics of the two groups (PVP-I mouthwash and placebo mouthwash. Group randomization will occur prior to the study visit using block randomization with block sizes randomly chosen as 4 or 6. Categorical variables will be described by frequencies, whereas continuous variables will be described using ranges, means, medians, and inter-quartile ranges and compared between groups using either the Chi-square test for binomial proportions or the Fishers' exact test as needed. Continuous variables will be compared using either a t-test for independent groups or the Mann-Whitney for cases where normality is not a reasonable assumption. All statistical tests will be two tailed, with an alpha level of 0.05.

Note that we may not be able to adjust for anything (or the adjustments will have to be very limited in scope and breadth) due to sample size issues.

Analysis of the Primary Efficacy Endpoint(s)

As described earlier, the primary endpoint is the percentage reduction of SARS-Co-V-2 load at 60 minutes (post-intervention) compared to baseline between the PVP-I mouthwash versus the placebo mouthwash. Assuming normality is a reasonable assumption, this percentage reduction will be compared between the two mouthwash groups (PVP_I versus placebo) using a t-test. Results will be presented as means and standard deviations with corresponding 95% confidence intervals and p-values.

Note that missing data should not be a concern as the cross-sectional study is a single visit.

Analysis of the Secondary Endpoint(s)

The secondary endpoints are the percentage reduction of SARS-Co-V-2 load at both 5 and 30 minutes (post-intervention) compared to baseline between the PVP-I mouthwash versus the placebo mouthwash. Assuming normality is a reasonable assumption, these respective percentage reductions will be compared between the two mouthwash groups (PVP_I versus placebo) using a t-test. Results will be presented as means and standard deviations with corresponding 95% confidence intervals and p-values.

Note that missing data should not be a concern as the cross-sectional study is a single visit.

Safety Analyses

Safety data will be collected at all study visit through solicitation of adverse events from subjects. Safety data will also be collected throughout the duration of the study via the subject's medical records.

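### The enrolment target is 44 in the sample-size section but 40 in the population and recruitment sections, and at the plan's own 20% dropout only 44 supports the stated 80% power

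*Combined protocol and SAP*

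**What the plan says.** The combined protocol and SAP gives the size of the trial in several places.

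- **Sample Size Determination, evaluable number:** "For the desired 80% power, the necessary sample size(s) is calculated to be n=34 (17 per arm").
- **Sample Size Determination, enrolled number:** "After accounting for the aforementioned 20% dropout, 44 patients will be enrolled in the study (22 per arm").
- **Target population, number randomized:** "Forty (40) subjects with confirmed clinical diagnosis of COVID-19 and at least one onset clinical sign will be recruited and randomized in the study". The entry for subjects enrolled by Penn researchers, directly below, is also 40.
- **Subject recruitment, number enrolled:** "COVID-19+ patients will be recruited to achieve 40 study subjects who enroll in and are eligible for study participation".

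Three other statements bear on how these fit together. Target population allows more than 40 people to consent if some fail screening. It also allows, at the investigators' discretion, replacement of subjects who were randomized, received product and then withdrew or were discontinued; poor samples are the example given. The sections on analysis of the primary and secondary endpoints say that missing data should not be a problem, because this part of the study is a single visit.

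**The concern.** Both numbers are meant to be final. The 44 already includes the allowance for dropout, so it is a count of patients entering the trial. The 40 is described as the number randomized, with screen failures counted separately, so it too is a count of patients entering the trial. They cannot both be right.

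Two things follow. First, the 80% power statement belongs to a trial of 44, while the operative sections describe a trial of 40. If 20% are lost from 40, the evaluable number falls below the plan's own minimum. Second, the target decides when enrolment stops, how long the randomization list must be and what completed enrolment is judged against. A trial that stops at 40 looks four short to a reader of the statistical section; one that reaches 44 looks over-enrolled to a reader of the recruitment section.

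**Working it through.** **Inputs, from Sample Size Determination unless noted**

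- Type I error: "Alpha (probability of Type-I error [true null hypothesis is rejected]) of 0.05"; two-sided, from General Approach: "All statistical tests will be two tailed, with an alpha level of 0.05".
- Target: "Power (probability of rejecting a false null hypothesis) of 0.80".
- Effect: "by assuming a 20% greater difference (PVP-I versus placebo) in the reduction of SARS-Co-V-2 load after 60 minutes". I read this as an absolute difference of 0.20, on the same scale as the SD.
- SD: 0.20 in both arms, so the standardized difference is d = 0.20/0.20 = 1.
- Test: two-sample t-test with equal variances and equal arms.
- Dropout: 20%.

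**Step 1. Reproduce the evaluable number.** With n per arm, the test has 2n − 2 degrees of freedom and noncentrality d × √(n/2). Power is the probability that a noncentral t variable with these parameters exceeds the two-sided 5% critical value in absolute size.

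| n per arm | df | Noncentrality | Critical t | Power |
|---|---|---|---|---|
| 16 | 30 | 2.828 | 2.042 | 0.781 |
| 17 | 32 | 2.915 | 2.037 | 0.807 |
| 18 | 34 | 3.000 | 2.032 | 0.830 |
| 20 | 38 | 3.162 | 2.024 | 0.869 |
| 22 | 42 | 3.317 | 2.018 | 0.900 |

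The smallest n with at least 80% power is 17 per arm, 34 in total. The plan's figure reproduces.

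**Step 2. Reproduce the enrolled number.** Enrolled per arm = evaluable per arm / (1 − dropout) = 17/0.8 = 21.25, rounded up to 22, so 44 in total. This also reproduces.

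**Step 3. Look for a route to 40.** Inflating the total gives 34/0.8 = 42.5, so 43. Multiplying by 1.2 instead of dividing by 0.8 gives 17 × 1.2 = 20.4, so 21 per arm (42), or 34 × 1.2 = 40.8, so 41 in total. None of these gives 40.

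**Step 4. Apply the plan's dropout to each target.**

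- From 44: 44 × 0.8 = 35.2 evaluable, above 34.
- From 40: 40 × 0.8 = 32 evaluable (16 per arm), two below 34. Power is 0.781.

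If each patient is lost independently with probability 0.20, average power is 0.776 from 40 and 0.817 from 44. The chance of ending with fewer than 34 evaluable is then about 71% from 40 and about 25% from 44 (binomial with retention 0.8).

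**Step 5. Find the loss that 40 can absorb.** 1 − 34/40 = 0.15. Forty randomized leaves 34 evaluable if loss is 15% or less. With no loss (20 per arm), power is 0.869.

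**The case against.** The strongest reply is that the shortfall may never happen. The primary endpoint is measured 60 minutes after one rinse at one visit, the analysis sections expect little missing data, and lost subjects or poor samples can be replaced. On those terms 40 randomized could well give 34 or more evaluable patients, and with no loss it beats the planned power. Even in the bad case the deficit is 1.9 points (80.0 − 78.1), from one patient per arm. The normal approximation still gives 80.7% at 16 per arm. The assumed SD matters more: at the full 17 per arm, an SD of 0.21 gives 76.8% and 0.22 gives 72.9%.

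Much of this stands. The power loss is small, and it depends on heavy loss without replacement. It does not reconcile the targets, for three reasons.

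- Replacement is optional, and the sample-size section does not rely on it, so it cannot guarantee 34.
- An expectation of negligible missing data sits badly with a planned 20% dropout in the same document. That is a further reason to settle the assumption.
- The normal approximation is not the plan's method. The plan names a t-test, and its 17 per arm is the t-test answer; the approximation would have given 16.

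It is also fair to say that no single calculation is wrong: 34 and 44 are both correct. The fault is that 44 and 40 appear in one plan as the same quantity.

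**Conclusion.** The concern holds. The statistical section and the operative sections give different numbers of patients to be entered, 44 and 40, and nothing in the documents reconciles them. Under the plan's own assumptions (difference 0.20, SD 0.20, two-sided 5% t-test, 20% dropout), 80% power goes with 44. From 40, the same dropout leaves 32 evaluable and 78.1% power.

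The targets differ by four patients, and the consequence is about two evaluable patients and two points of power. That consequence assumes the full 20% loss with no replacement; at 15% loss or less, 40 is enough. This should be corrected because it is a plain contradiction in a figure that the trial relies on, and not because the trial would be seriously underpowered.

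**What to change.** State one randomization target and use it in Target population, in the entry for subjects enrolled by Penn researchers, in Subject recruitment and in Sample Size Determination. The sponsor should say which number is intended.

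- **If 40:** in Sample Size Determination, replace 44 (22 per arm) with 40 (20 per arm). Then state either 78% power at 20% dropout, or 80% power at up to 15% loss. The second fits a single-visit Phase I better, but 15% is simply what 40 allows, so the plan should say why it is reasonable. If replacement is relied on to keep 34 evaluable, make it a stated rule and say so here.
- **If 44:** change 40 to 44 in the population and recruitment entries, and leave the sample-size section as it is.

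The first option costs a text edit in one section and needs no extra enrolment; the price is a slightly lower stated power or a lower dropout assumption. The second costs edits in the population and recruitment sections and four more patients.

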Title:	Povidone-Iodine Oral Rinse Study: A 2-phase, Randomized Trial to Test the Effects of Povidone-iodine 0.5% as Mouthwash/Gargle on SARS-CoV-2 (COVID 19) Load as an Adjuvant Infection Control Measure in Dental Practice
Brief Title:	Povidone-Iodine Oral Rinse Study
NCT Number:	05239598
IRB Number:	849386
Version Date:	5/13/2022

Protocol

Abstract

This study is a two-arm, randomized, 2-phase study. Phase I will be double blinded clinical trial of the safety and efficacy of an antiseptic mouth rinse solution on reducing SARS-CoV2 load in COVID 19+ adult individuals. Phase II is designed as an open label trial, and all subjects will receive the active mouthwash.

Objectives

Overall objectives

Primary Objective: is to test the efficacy of Povidone-iodine 0.5% when used as a mouth rinse on reducing SARS-CoV-2 load in the oral cavity of COVID-19+ individuals.

Primary outcome variable(s)

The primary outcome is the change in amount of SARS-CoV-2 in the oral cavity before and after intervention.

Secondary outcome variable(s)

Subjects clinical status at day 7 and the number of COVID-19 symptoms, symptoms onset and the severity of symptoms will be collected throughout Phase 2 of the study.

Background

Severe acute respiratory syndrome, or SARS is caused by a novel coronavirus termed the SARS coronavirus, or SARS-CoV-2, spreads through droplet infection produced when the infected person speaks, coughs, or sneezes, and affects people of any age. The epidemic of coronavirus disease 2019 (COVID-19) caused by SARS-CoV-2, originating in Wuhan, China, has become a major public health challenge for not only China but also countries around the world. [1] The disease has affected vulnerable individuals, especially those with co-morbidities. [1]

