All subject reported and evaluator observed adverse events will be collected documented on the appropriate CRF. Only related adverse events will be reported for this research study. Expected related adverse events include gingival/mucosal irritation and allergic reaction to study products.

Baseline Descriptive Statistics

Baseline (including demographic) characteristics will be summarized by standard descriptive statistics (including mean and standard deviation for continuous variables such as age and standard percentages for categorical variables such as gender). This will be done for both the overall cohort and stratified by mouthwash solution (antiseptic versus placebo). The baseline characteristics will be compared across the two mouthwash groups using Fisher's Exact test for categorical variables and t-tests for continuous variables (also accounting for equal versus unequal variance across the groups).

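### Safety Analyses records all adverse events but limits reporting to related ones; read as a rule for results, this lets an undefined causality judgement decide which harms are shown

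*Combined protocol and SAP*

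**What the plan says.** Under Safety Analyses, collection is broad. Adverse events are solicited from participants ("Safety data will be collected at all study visit through solicitation of adverse events from subjects"), and medical records are a second source ("Safety data will also be collected throughout the duration of the study"). Everything found goes on the form: "All subject reported and evaluator observed adverse events will be collected documented on the appropriate CRF".

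The next sentence narrows this: "Only related adverse events will be reported for this research study". The section then closes with the events that are anticipated: "Expected related adverse events include gingival/mucosal irritation and allergic reaction to study products". It does not say who judges relatedness, by what criteria or when, and it describes no display of adverse events.

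The Abstract gives safety a place among the aims: "Phase I will be double blinded clinical trial of the safety and efficacy of an antiseptic mouth rinse solution". Safety does not appear under Objectives or among the endpoints.

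**The concern.** The plan gathers harms regardless of cause and then appears to show only those that someone has attributed to the rinse. If that is the rule for results, the safety account depends on a judgement the plan does not define, and unrelated events that were duly recorded never reach the reader.

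Attribution for the individual patient is weak in this population. Every participant enters with symptomatic COVID-19, and a product effect in the mouth or throat may look like the disease. Randomization is the design's protection against this problem, because an excess of all-cause events in one arm needs no attribution. A related-only rule gives that protection up. At stake is the safety half of what the Abstract says Phase I is for.

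**Working it through.** No figure in the documents attaches to this point, so the check sets the sections side by side.

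1. **Scope of collection against scope of reporting.** Both statements are in Safety Analyses, in consecutive sentences. The first covers all events, the second only related ones. No other section says what happens to recorded events judged unrelated.

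2. **What *reported* refers to.** The sentence sits under an analysis heading within Statistical Considerations, which favours a rule for results. Elsewhere the plan uses other verbs for results. For efficacy: "Results will be presented as means and standard deviations with corresponding 95% confidence intervals and p-values". For baseline data: "characteristics will be summarized by standard descriptive statistics". The sentence after the restriction lists expected related events, which is also how a notification rule might continue. Neither reading can be proved from the text.

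3. **How reliable attribution can be.** The symptom list in Key inclusion criteria includes sore throat, nausea or vomiting, and new loss of taste or smell. The expected related events in Safety Analyses include mucosal irritation. A throat complaint after rinsing could be assigned to either cause. If it is put down to COVID-19, a related-only display omits it in both arms, and any excess on povidone-iodine disappears with it.

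4. **Where a randomized comparison exists.** Per the Abstract, Phase I is randomized and double blinded, while Phase II is open label with everyone on active product. Per Procedures, those not continuing leave after Visit 1, and continuers, former placebo participants included, are given active product to take home. The by-arm comparison therefore belongs to the Phase I visit, where the last scheduled sample is 60 minutes after the rinse. Phase II has no control.

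5. **Who belongs in the denominator.** Target population allows participants who received product and then left to be replaced at the investigator's discretion. A Phase I safety table should still count them.

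6. **Effect on the rest of the plan.** The inputs under Sample Size Determination are a difference and a standard deviation in viral load reduction, alpha, power and dropout. None involves adverse events, and the efficacy analyses do not use them.

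**The case against.** The strongest reply is that *reported* means notification to an oversight body. The choice of verbs and the sentence that follows give this some support. If it is right, nothing is withheld from the results, and what remains is that no adverse event table is described. That omission alone would be missing detail and not a flaw. General Approach already describes categorical variables by frequencies, which could be stretched to cover adverse events, although that paragraph concerns characteristics of the two groups and does not name them. This reply stands as a possible reading, and it is why the sentence needs clarifying whichever meaning was intended.

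A reader might also infer that harms would be filtered by assessors who know the treatment. The documents do not support this for Phase I, which is double blinded. In Phase II treatment is known, but everyone receives the same product, so there is no contrast between arms to distort. The limitation there is the lack of a control, and no table cures that.

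Nor do the documents show that a given share of events would be lost, or that seriousness and severity are recorded for each adverse event. The severity mentioned under Secondary outcome variable(s) and Procedures is that of COVID-19 symptoms.

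Finally, safety is not a formal objective or endpoint, and a single supervised rinse may produce few events. Both are fair, and they limit the weight of the point without removing it.

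**Conclusion.** The point holds in a limited form. As written and where it stands, the sentence makes the display of recorded harms depend on a causality judgement without a stated rule, and forgoes the all-cause comparison by randomized arm in Phase I. This rests on taking *reported* to refer to results, which is the natural reading under that heading but not the only one. A reader should not conclude that the sponsor certainly intends to withhold unrelated events, or that Phase I causality would be judged unblinded; the text establishes neither.

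The number of events affected cannot be estimated from the documents. The consequence is confined to the safety account. The change should be made, but the primary and secondary efficacy conclusions do not depend on it.

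**What to change.** Replace the restricting sentence with:

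> All adverse events recorded on the CRF will be tabulated descriptively, by randomized arm for Phase I (all who used the assigned rinse, including any later replaced; events up to the end of the Phase I visit) and overall for participants who continue into Phase II, with events judged related shown as a subset.

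Show seriousness and severity if the CRF records them. If the related-only rule was meant for notification, keep it as a separate sentence that says so.

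The cost is one revised sentence and a descriptive table from events already being documented. The table will contain background COVID-19 symptoms, some of which repeat the Day 7 questionnaire for those who continue. It supports description only, not a test. The Phase I by-arm window is short, and a reaction to the assigned rinse that begins after the visit falls outside it. Listing the Phase I arm beside each Phase II event would keep such a reaction traceable for participants who continue.
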